## 5.6 End of Treatment Visit (7 [+3] Days after the Last Dose of ARQ 087)

If possible, the End of Treatment Visit should be performed 7 [+3] days after the last dose of ARQ 087. The following assessments will be made during the End of Treatment Visit:

- Physical examination, including mucous membranes and skin
- ECOG PS
- Vital signs (weight, temperature, blood pressure, respiration rate, and pulse)
- Fasting clinical blood tests (see Section 6.4)
- Urinalysis (see Section 6.4)
- Serum pregnancy test, if applicable (see Section 6.4)
- 12-lead ECG (see Section 6.3)
- Echocardiography or MUGA scan to measure LVEF, if applicable (see Section 6.3)
- Blood samples for tumor marker(s), if applicable (to be tested at study site)
- Blood samples for pharmacokinetics (except Expanded Cohort, see Section 6.5)
- Tumor measurement and staging if not done within four weeks (28 days) prior to the end of treatment visit (see Section 6.7)
- AEs assessment
- Record concomitant medications

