3.2.4 Efficacy Variables

Best Overall Response (BOR)

The best overall response is determined once all the data for the subject is known. No confirmatory measurement for CR or PR is required in this study. The best overall response is defined as the best response (in the order of CR, PR, SD, and PD) among all overall responses recorded from the start of treatment until the last radiographic tumor assessment (for example, a subject who has SD at first assessment, PR at second assessment, and PD on last assessment has a best overall response of PR). When SD is believed to be the best response, it must also meet the protocol specified minimum time from baseline, 8 weeks (± 3). If the minimum time is not met when SD is otherwise the best time point response, the subject's best response depends on the subsequent assessments. For example, a subject who has SD at first assessment, PD at second and not meeting minimum duration of SD will have a best response of PD. The same subject lost to follow-up after the first assessment would be considered non-evaluable.

Objective Response Rate (ORR)

For purposes of determining the objective response rate (ORR), tumor response will be based on the best overall response recorded for each subject from the date of first dose. The ORR will be calculated as the number of subjects with a complete or partial response divided by the total number of subjects [ORR= (CR+PR)/# subjects].

Disease Control Rate (DCR)

Disease Control Rate (DCR) is defined as the proportion of subjects with the best overall responses of CR, PR and SD [DCR= (CR+PR+SD)/# subjects].

Duration of Objective Response

Duration of objective response is defined as the time from the date of the measurement criteria are first met for CR/PR (whichever is first recorded) until the first date that recurrent or progressive disease is documented.

If a subject is discontinued, dies, or is lost to follow-up with no documentation of progressive disease, duration of response is defined as the time from the date of the first documentation of objective response to the date of the last tumor assessment as a censored value. Duration of response will be measured for responding subjects (PR or CR) only.

Duration of Stable Disease

Duration of stable disease is defined as the time from the start of the treatment until the criteria for disease progression are met.

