If a subject is discontinued or dies, or is lost to follow-up with no documentation of progressive disease, duration of stable disease is defined as the time from the date of first dose to the date of the last tumor assessment as a censored value. Duration of stable disease is measured for any subject who has best overall response of SD.

Progression-Free Survival (PFS)

Progression Free Survival (PFS) is defined as time from first dose until documented radiographic disease progression or death, whichever occurs first.

If a subject is discontinued from study due to reasons other than radiographic disease progression or death, PFS is censored as the time from the date of first dose to the date of the last tumor assessment. Only assessments with CR, PR SD or NE as overall tumor response are treated as last tumor assessment.

If a subject has no baseline tumor assessment and/or has no post baseline tumor assessment, this subject is to be censored at the date of first dose for PFS.

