4.4 Evaluable Population

Subjects who have received at least one cycle of study treatment and have at least one post-baseline tumor evaluation are included in the evaluable population.

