5.2 General Statistical Considerations

All summary tables will include all subjects from cohort 1 to the last cohort enrolled and be presented by treatment groups, including low dose group (25 mg QOD – 200 mg QD), middle dose group (250 mg QD – 325 mg QD), high dose group (400 mg QD - 425 mg QD), expanded (RP2D) cohort (300 mg QD) and Overall.

Categorical variables will be summarized as the number and percentage of subjects in each category. Continuous variables will be summarized as mean, standard deviation, median, minimum and maximum.

As appropriate, all data collected on the electronic case report form (eCRF) will be presented in listings. All statistical analyses will be performed using SAS® version 9.2 or higher.

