5.4.5 Efficacy Analyses

Efficacy analysis will be performed based on both safety and evaluable populations.

Objective Response Rate and Disease Control Rate

The best overall tumor response (CR, PR, SD, PD and not evaluable), objective response rate and disease control rate will be tabulated by treatment group and overall on the safety population and evaluable population. The percent of subjects in each treatment group will be provided along with the 95% confidence interval of the percentage. In addition, the related listings will also be presented.

Percent change from the minimum sum of longest diameters (including baseline, if that is the minimum value, up to the preceding tumor assessment) and the percent change from baseline for the sum of longest diameters will be computed in the listings for target lesions. A waterfall plot will also be utilized to display the relationship between minimum sum of longest diameters change and current cancer types.

Progression Free Survival

Progression free survival will be estimated based on Kaplan-Meier estimate (product limit) for both safety and evaluable population. The median PFS and the 95% confidence interval will be estimated, and the corresponding Kaplan-Meier plots will be also presented.

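### The last PFS sentence in SAP 3.2.4 censors unscanned subjects at first dose with no exception for death, so the safety-population PFS can lose early deaths that the definition counts as events

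*SAP*

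**What the plan says.** Three statements on PFS follow one another in SAP 3.2.4.

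- Definition: "Progression Free Survival (PFS) is defined as time from first dose until documented radiographic disease progression or death, whichever occurs first". Protocol 10.2.3 defines PFS in the same way.
- General censoring: "If a subject is discontinued from study due to reasons other than radiographic disease progression or death, PFS is censored" at the last tumor assessment. Death is exempt here.
- No-scan rule: a subject with no baseline assessment and/or who "has no post baseline tumor assessment, this subject is to be censored at the date of first dose for PFS". Death is not exempt here.

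SAP 5.4.5 plans two PFS analyses: "Progression free survival will be estimated based on Kaplan-Meier estimate (product limit) for both safety and evaluable population". The safety population (SAP 4.2) is everyone who took any drug. The evaluable population (SAP 4.4) is limited to subjects who completed at least one cycle and "have at least one post-baseline tumor evaluation are included in the evaluable population". SAP 5.2 adds that "All summary tables will include all subjects from cohort 1 to the last cohort enrolled and be presented by treatment groups".

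SAP 6.1.1 deals only with partial scan dates, and SAP 9 lists no changes. Neither says which of the three statements prevails.

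**The concern.** The first scheduled post-baseline scan is at week 8 (Protocol 6.7 and Appendix 6). A dosed subject who dies earlier without an unscheduled scan meets both the event definition and the no-scan rule. Two programmers could follow the SAP faithfully and report different PFS from the same data.

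If the no-scan rule wins, the earliest deaths leave the safety-population curve, and the estimate can move only in the drug's favour. PFS is one of the measures that Protocol 10.2.3 names as preliminary evidence of activity. The safety population is also the only planned PFS population that could show these deaths.

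**Working it through.** **1. One subject, two readings.** Take a subject dosed on Day 1 who dies in week 5 with no post-baseline scan.

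| Analysis | Definition governs | No-scan rule governs |
|---|---|---|
| Safety population | event at week 5 | censored at time 0: no event, no time at risk |
| Evaluable population | not included (SAP 4.4) | not included (SAP 4.4) |

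The disputed sentence therefore changes the safety-population analysis only. Under the literal reading, these subjects are lost from the safety analysis just as they are from the evaluable one.

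**2. Can the group exist?** Clinically indicated scans (Protocol 6.7), the End of Treatment scan and the effort to document progression after stopping (Appendix 6) all shrink it. They do not empty it.

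- A subject who dies on treatment has no End of Treatment visit.
- That visit requires "Tumor measurement and staging if not done within four weeks (28 days) prior to the end of treatment visit", and the text does not say that the earlier scan must be post-baseline. Suppose the baseline scan is b days before Day 1, the last dose is on Day L, and the visit is 7 to 10 days later. The baseline scan waives the new one when (L − 1) + 7 + b ≤ 28, so L ≤ 22 − b. With 10 days, L ≤ 19 − b. For b = 0 that means a last dose up to Day 19–22; for b = 14, up to Day 5–8.

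The no-baseline branch should be nearly empty, because baseline imaging is required (Protocol 5.2, Appendix 6).

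**3. Size on the curve.** The documents give no PFS sample size, event count or early-death rate, so there is no plan figure to reproduce. Let n be the number of subjects, k the unscanned early deaths, and d the other events before week 8.

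- Literal rule, just before week 8: S = 1 − d/(n − k).
- Deaths as events: S = 1 − (k + d)/n.
- Difference = (k/n) × [1 − d/(n − k)], which is k/n when d = 0.

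With n = 60 (upper end of the Expanded Cohort) and d = 0, S is 1.000 under the literal rule. With deaths counted it is 0.950 (k = 3), 0.900 (k = 6) or 0.800 (k = 12). With no other censoring, later values are multiplied by (n − k)/n. For an assumed 24-week median and k = 6, week-24 PFS goes from 0.500 to 0.500 × 54/60 = 0.450.

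**4. Size on the median.** With n = 60, progression read at 8-weekly scans and assumed medians of 16, 24 and 32 weeks, the Kaplan-Meier median is unchanged at k = 3 and k = 6 in all three cases. It drops by one scan interval only at k = 12 (24-week case) and at k = 9 and 12 (32-week case).

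A simulation gives the same picture. Assumptions: n = 60, independent exponential progression (median 20 weeks) and death (median 52 weeks), 8-weekly scans, no other dropout, 3,000 replicates per setting. The share dead by week 8 is 1 − 0.5^(8/52) = 10.1%. Ranges are over repeated runs.

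| Share of those deaths unscanned | Mean k | Mean shift in median (weeks) | Median unchanged |
|---|---|---|---|
| 25% | 1.5 | 0.6–0.7 | about 74% of trials |
| 50% | 3.0–3.1 | 1.1–1.2 | 61–64% |
| 100% | 6.0–6.1 | 2.2–2.3 | 44–47% |

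The mean median is about 17.0 weeks, with a mean 95% confidence interval of about 12.2 to 23.6 weeks.

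**5. Small groups.** The Middle Dose Group (cohorts 7 and 8, 3–6 subjects each) has 6–12 subjects. One unscanned death there is 1/12 = 8.3% to 1/6 = 16.7% of the group, and the early curve is overstated by that much when d = 0. The median says little at this size: its simulated interval at n = 12 is about 7 to 36 weeks.

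**The case against.** The strongest reply is that the drafter never meant to censor deaths. The PFS text makes death an event and exempts it from general censoring. The last sentence may only supply a censoring date when no last assessment exists. Where SAP 3.2.4 does censor deaths, it says so: "If a subject is discontinued, dies, or is lost to follow-up with no documentation of progressive disease, duration of response is defined" as a censored value, and duration of stable disease is worded likewise. This reading is plausible, and under it there is no bias. A reader might infer from the last sentence that the plan intends to censor early deaths, and the documents do not support that. What stands is that the sentence is an unqualified instruction and nothing ranks it below the definition.

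A reader might also infer that this sentence spoils both PFS analyses. It does not: the evaluable analysis omits subjects without a post-baseline scan through SAP 4.4, whatever this sentence says.

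A third objection is that few subjects are affected. Eligibility requires a life expectancy of at least 12 weeks and ECOG of 2 or less (Protocol 3.1). These criteria make early deaths less likely but do not prevent them. The 10.1% used above is an assumption.

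Finally, nothing is decided on PFS. The primary objective is safety, no hypothesis is tested (SAP 5.1), and the iCCA enrolment rule uses response (SAP 7). Early deaths remain visible among TEAEs resulting in death (SAP 5.4.7), and these subjects stay in the safety-population ORR and DCR denominators. All of this stands, and it limits the weight of the point.

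**Conclusion.** The point holds for the safety-population PFS. The text gives two answers for a subject who dies unscanned, and the literal one departs from the SAP's and the protocol's own definition. Any bias is upward. On the curve before week 8 it is at most k/n. Since the documents do not give k, every figure above rests on assumed counts and assumed event times.

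A stronger reading would be that median PFS is materially inflated. In continuous time with an exponential curve, counting 5% or 10% early unscanned deaths multiplies the literal median by 1 + log2(0.95) = 0.926 or 1 + log2(0.90) = 0.848. Those ratios should not be carried over to this trial, where most events are read at 8-weekly scans. The median then often stays put, and the mean shifts are well inside its confidence interval. This is a minor correction, worth making because the ambiguity concerns the endpoint's own event and is easily removed.

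**What to change.** Replace the last PFS sentence of SAP 3.2.4 with:

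> Subjects with no baseline and/or no post-baseline tumor assessment are censored at the date of first dose only if they have neither documented radiographic progression nor a recorded death; otherwise PFS is an event at the earlier of the two.

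Report the number of subjects censored at first dose, by treatment group. State beside the evaluable-population PFS that it excludes early unscanned deaths by design; the new wording does not change it for subjects without a post-baseline scan.

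The cost is one SAP sentence, one programming condition and one added count. No protocol amendment is needed, because the wording restores the definition in Protocol 10.2.3. Deaths up to 30 days after the last dose are already collected, including fatal disease progression (Protocol 8.1.7 and 8.5). Collection stops when another anticancer therapy starts (Protocol 5.7, 8.1.7 and 8.5). A later death may therefore go unrecorded, and that unscanned subject would stay censored at first dose. The downside is that reported PFS may be slightly less favourable.

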4 STATISTICAL ANALYSIS POPULATIONS

Four populations are considered in the statistical analysis of the study. The treatment cohort assignment for analyses on all populations will be based on the dose they received.

4.1 Enrolled Population

Subjects who enrolled in ARQ 087-101 study are included in the enrolled population.

4.2 Safety Population

Subjects who received any amount of ARQ 087 are included in the safety population.

4.3 Pharmacokinetic Population

Subjects who received at least one dose of ARQ 087 and who had an evaluable ARQ 087 pharmacokinetic profile on first day (Week 0 Day 1/Cycle 1 Day 1) and/or last day (Cycle 1 Day 22/23) in treatment cycle 1 are included in PK population.

4.4 Evaluable Population

Subjects who have received at least one cycle of study treatment and have at least one post-baseline tumor evaluation are included in the evaluable population.

5 STATISTICAL METHODS AND DATA ANALYSIS

5.1 Determination of Sample Size

No formal statistical tests of hypotheses will be performed in this study. The exact number of subjects estimated for this study depends on the number of cohorts investigated based on the toxicity encountered. It is expected that approximately 60-120 subjects will be enrolled in this study.

5.2 General Statistical Considerations

All summary tables will include all subjects from cohort 1 to the last cohort enrolled and be presented by treatment groups, including low dose group (25 mg QOD – 200 mg QD), middle dose group (250 mg QD – 325 mg QD), high dose group (400 mg QD - 425 mg QD), expanded (RP2D) cohort (300 mg QD) and Overall.

Categorical variables will be summarized as the number and percentage of subjects in each category. Continuous variables will be summarized as mean, standard deviation, median, minimum and maximum.

As appropriate, all data collected on the electronic case report form (eCRF) will be presented in listings. All statistical analyses will be performed using SAS® version 9.2 or higher.

5.3 Visit Window Rules

If there are multiple measurements/samples within the same post-baseline visit, the last measurement/sample within the visit (sorted by date and as available by time or repeat measurements) will be used in the analysis by visit or overall. For any analyses, only scheduled visits will be included except for using value from unscheduled visit as baseline if needed.

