#### **4.6 Study Duration**

Subjects will receive treatment with ARQ 087 until progression of disease (clinical or radiological), unacceptable toxicity, or another of the discontinuation criterion is met (see Section 5.8). It is expected that most subjects will receive between one and six cycles of ARQ 087 for a treatment period of four to 24 weeks.

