**Table 7.1 Dose Delays/Reductions for Drug-Related Toxicity**

Event Grade	Action
Grade 1 or 2, including significant increase in LFTs (as assessed by the Investigator) and alopecia	Continue current dose level, unless dose interruption/modification may be clinically indicated, e.g., due to significant increase in LFTs
Grade 3-4 nausea, vomiting or diarrhea lasting < 24 hours	Withhold ARQ 087 until recovery to Grade 1 or baseline. If recovery occurs within 24 hours, restart ARQ 087 at the current dose level.
Grade 3-4 toxicity, including nausea, vomiting or diarrhea lasting $\geq$ 24 hours	
Withhold ARQ 087 until recovery to Grade 1 or baseline.
 
 
- If recovery occurs within 14 days, restart ARQ 087 at the dose and schedule of the previous cohort for all subsequent cycles, unless further dose reduction is required.
 
- If recovery occurs within 21 days of the drug hold, ARQ 087 may be restarted upon agreement between the Investigator and the Sponsor's Medical Monitor. Treatment should be restarted at the dose and schedule of the previous cohort for all subsequent cycles, unless further dose reduction is required.
 
- If recovery occurs after more than 21 days of the drug hold, ARQ 087 should be permanently discontinued
 

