### 7.7.2 Prohibited Treatment/Treatment to Be Avoided or Used with Caution

The following treatments are not allowed during the study:

- Any concurrent anti-cancer therapy including chemotherapy, radiotherapy, hormonal, targeted therapy, or immunotherapy
  - Palliative radiotherapy for local pain-control may be allowed, provided the subject does not meet criteria of progressive disease and treated lesions will not be included in the target/non-target lesion assessment
- Other investigational agents
- Immunosuppressive therapies, including systemic corticosteroids (except up to a 25 mg/day prednisone-equivalent dose or when used intermittently in an antiemetic regimen, for CNS metastases management or as premedication for imaging studies)

The following treatments should be avoided, if possible or used with caution during the study:

- ARQ 087 may inhibit CYP1A2 or CYP2D6 metabolism, hence co-administration of ARQ 087 with drugs known to be substrates of CYP1A2 or CYP2D6 should be avoided or used with caution (see Appendix 4)
- ARQ 087 may be a substrate and inhibitor of human P-glycoprotein (P-gp), therefore co-administration of ARQ 087 with drugs known to be P-gp substrates with narrow therapeutic index should be avoided or used with caution (see Appendix 5)
- Drugs with known liver toxicity, e.g., clotrimazole, should be avoided or used with caution; if such drugs need to be administered, LFT should be done every 4-5 days during the drugs' co-administration

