### 8.1.7 Further Adverse Event and Serious Adverse Event Defining

Wherever possible, a specific disease or syndrome rather than individual associated signs and symptoms should be identified. However, if an observed or reported sign or symptom is not considered a component of a specific disease or syndrome by the Investigator, it should be recorded as a separate AE.

Laboratory data are to be collected as stipulated in this protocol. Clinical syndromes associated with laboratory abnormalities are to be recorded as appropriate (e.g., diabetes mellitus instead of hyperglycemia).

Scheduled hospitalizations or elective surgical procedures will not be considered as AEs or SAEs.

Prolongation of a scheduled hospitalization can be considered an SAE.

Complications associated with scheduled procedures are considered AEs or SAEs.

Progression of disease is considered an efficacy outcome parameter and should not be captured as an AE or a SAE unless its outcome is death.

Adverse events including SAEs that occur following the execution of the ICF but prior to dosing will not be recorded as AEs or SAEs.

Adverse events including SAEs that occur after subjects receive any anticancer therapy other than the study-defined treatments will not be recorded as AEs or SAEs.

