Summary statistics for baseline, each post-baseline measurement, and change from baseline for each post-baseline measurement will be presented for all parameters in the safety population.

Toxicities will be graded according to the NCI CTCAE, Version 4.03. Shift table of toxicity grade for NCI CTCAE specified laboratory tests will also be presented in the safety population per treatment groups and overall.

Baseline is defined as the last non-missing value assessment made prior to the first dose of study medication, which is, for most subjects, the clinical laboratory assessment taken on Day 1 prior to the first dose. If it's missing, the laboratory assessment at screening (including pre-study visit and unscheduled visit) will be used as baseline value.

If lab results contain symbols like "<", ">", "≥" or "≤", extract the numeric value as the limit, Example: if result is ">0.1", "0.1" will be used for analysis.

Vital Signs

Summary statistics for baseline, each post-baseline measurement, and change from baseline for each post-baseline measurement will be presented for each vital sign parameter.

Individual absolute vital sign values and the change from baseline will be summarized descriptively for each treatment group and overall, by schedule of assessments.

ECOG Performance Status

Number and percentage of subjects having each ECOG performance status level will be presented for baseline and each post-baseline measurement, per treatment groups and overall.

In addition, the shift table comparing post baseline to baseline will also be presented per treatment groups and overall.

12-lead ECG

12-lead ECG absolute individual parameters [PR interval, QRS interval, QT interval, QTcF interval, QTcB interval and Summary (Mean) Ventricular Rate] and the change from baseline will be summarized per treatment groups and overall per assessment. All ECG measurements will be presented in the data listings.

Physical Examination

Data from physical examinations will be presented in the data listings as per subject per visit per body system, using safety population.

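### SAP 5.3 restricts all analyses to scheduled visits and the last value per visit, so the CTCAE laboratory shift table, which defines no post-baseline value, can leave out a recorded higher grade

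*SAP*

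**What the plan says.** SAP 5.3 (Visit Window Rules) contains two rules.

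- Scheduled visits: "For any analyses, only scheduled visits will be included except for using value from unscheduled visit as baseline if needed".
- Several values in one post-baseline visit: the last one "will be used in the analysis by visit or overall".

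SAP 5.4.7 (Laboratory Test) then plans the display at issue: "Shift table of toxicity grade for NCI CTCAE specified laboratory tests will also be presented in the safety population", by treatment group and overall. It does not say which post-baseline value supplies the grade. For baseline it is explicit. If the Day 1 pre-dose value is missing, "the laboratory assessment at screening (including pre-study visit and unscheduled visit) will be used as baseline value".

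The protocol provides for laboratory tests outside the visit schedule. Where drugs with known liver toxicity are co-administered, Protocol 7.7.2 says that "if such drugs need to be administered, LFT should be done every 4-5 days". Protocol 6.4 schedules coagulation tests, thyroid tests and HbA1c at Baseline and End of Treatment only, with further tests on clinical indication.

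**The concern.** Safety and tolerability is the primary objective, and the shift table is the planned summary of graded laboratory change. Tests outside the schedule tend to be drawn because someone is worried, or because a risk such as a hepatotoxic co-medication calls for closer watching. A rule that removes those values, and prefers the last value in a visit to the highest, tends to make graded laboratory toxicity look milder than the recorded data show.

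The treatment of unscheduled values is also uneven. One may set the grade a subject starts from, but may not set the grade the subject moves to.

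**Working it through.** The documents give no figure on this point, so there is none to reproduce. The check is a comparison of texts.

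**1. Does 5.3 reach the shift table?** The scheduled-visit rule covers all analyses and names baseline as its one exception. The last-value rule covers overall analyses as well as by-visit ones. SAP 5.4.7 contains no exemption and no definition that would displace 5.3. A programmer following the text would therefore use scheduled visits only and the last value in each.

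**2. What drops out?** Two invented cases, both with baseline Grade 0:

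| Recorded post-baseline grades | Highest grade available to the table under 5.3 | Worst recorded grade |
|---|---|---|
| Scheduled 1, unscheduled 3, scheduled 1 | 1 | 3 |
| Same visit: first draw 3, repeat 1 | 1 | 3 |

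A test drawn on clinical indication at a scheduled visit is kept, unless a later value in that visit replaces it.

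**3. Do off-schedule draws arise under the protocol?**

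- *Liver tests.* Every 4-5 days gives 28/5 = 5.6 to 28/4 = 7 draws per 28-day cycle. The schedule has four laboratory visits in Cycle 1 (Days 1, 8, 15, 22) and two in later cycles (Days 1, 15). If co-medication lasts a whole cycle, the draws exceed the scheduled number by 1.6 to 3 in Cycle 1 (5.6 - 4; 7 - 4) and by 3.6 to 5 later (5.6 - 2; 7 - 2). These are counts of draws, not of grades missed. The documents do not say how many subjects are concerned, and such drugs are to be avoided or used with caution.
- *Coagulation, thyroid, HbA1c.* Between Baseline and End of Treatment these are done only on clinical indication. The table covers only tests for which CTCAE specifies grades, and the SAP text does not list them.

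**4. Which visit does an extra draw belong to?** Despite its title, 5.3 gives no day ranges. The protocol's plus or minus 3 days governs when visits take place. If it were borrowed for analysis, Cycle 1 would be covered without gaps from Day 5 to Day 25 (5-11, 12-18, 19-25), so an extra draw there might be treated as a repeat. In later cycles, Days 5-11 and 19-25 would fall in no window. The SAP does not say whether this is intended.

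**5. Can the size be estimated?** For an abnormality lasting L days with random onset, and draws G days apart, the chance that no scheduled draw meets it is max(0, 1 - L/G). G is 7 in Cycle 1, 14 from Cycle 2, and optionally 28 after four cycles (Protocol 5.5.2). L is not in the documents. Assuming L = 7 with G = 7 gives 0; assuming L = 3 with G = 28 gives 1 - 3/28 = 89%. The loss due to 5.3 is this chance multiplied by the probability that an unscheduled test caught the abnormality, which is also unknown and could be zero. The formula counts episodes, whereas a shift table counts subjects, who lose nothing if a scheduled draw shows the same or a higher grade. A span this wide is not an estimate.

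**The case against.** **The table may not be meant to show the worst grade.** SAP 5.4.7 speaks only of a shift in toxicity grade. A visit-by-visit shift table on scheduled draws is ordinary and fits 5.3, and the table shells, whose content is not in the available SAP text, might define it. This stands in part. It cannot be said that the table fails a stated purpose. The supported defect is that the text leaves the post-baseline value undefined while 5.3 excludes recorded values from it.

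**Adverse event reporting already captures these results.** Protocol 8.2 has investigators assess events at non-scheduled visits with laboratory review. SAP 5.4.7 tabulates events at maximum grade, with separate Grade 3 or higher and DLT tables, and SAP 5.2 plans listings of eCRF data. This largely stands and limits the harm. It does not make the shift table redundant. Protocol 8.1.7 says "Clinical syndromes associated with laboratory abnormalities are to be recorded as appropriate (e.g., diabetes mellitus instead of hyperglycemia"), so an event may carry the grade of a syndrome and not that of the laboratory value, and listings are not summaries.

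**Stronger readings that a reader might infer:**

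- *That the last-value rule systematically replaces Grade 3-4 results with recovered ones*, because Protocol Table 7.1 says "Withhold ARQ 087 until recovery to Grade 1 or baseline". The table allows for recovery over as long as 14 or 21 days. A retest days later would more naturally be unscheduled or belong to the next visit, and 5.3 would then keep the high scheduled grade. Only a recovery retest recorded under the same visit would displace it.
- *That PFS or response is biased*, because an unscheduled scan would be dropped. SAP 3.2.4 takes best response from all recorded responses and PFS from documented radiographic progression or death, with no visit limit. It is the more specific text and would sensibly govern. Read with the same literalness, 5.3 would also exclude adverse events found at non-scheduled visits, which is plainly not meant. This is an ambiguity of scope.

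**Conclusion.** The point holds as a cheap improvement. As written, SAP 5.3 keeps unscheduled and superseded higher grades out of the CTCAE laboratory shift table, and SAP 5.4.7 does not define that table's post-baseline value. The effect is confined to the laboratory displays. It does not undermine the adverse event or DLT tables, and no bias in PFS or response is claimed.

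The direction for unscheduled tests is probably towards understatement, on the assumption that they are drawn because of a clinical concern. For repeats within a visit the direction is not guaranteed. The size in this trial is unknown, so no percentage is claimed. The conclusion rests on the available SAP text; a definition in the table shells could narrow it.

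**What to change.** Two sentences in the SAP:

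- In 5.3: *The scheduled-visit and last-value rules apply only to by-visit summaries.*
- In 5.4.7: *The laboratory shift table shows baseline grade to worst post-baseline CTCAE grade, using all scheduled, unscheduled and repeat values.*

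The first sentence also removes the literal conflict with SAP 3.2.4.

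No new data are needed: Protocol 12.2 has laboratory data recorded on the eCRF, and the SAP already allows unscheduled values as baseline. One table shell changes, and the reported laboratory grades may look slightly less favourable.
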